ERP	Event Related Potential
FDA	Food and Drug Administration
FTF	Fingertip-to-Floor Test
GCP	Good Clinical Practice
HAM-D	Hamilton Psychiatric Rating Scale for Depression
HIPAA	Health Insurance Portability and Accountability Act
HRV	Heart Rate Variability
Hz	Hertz
ICF	Informed Consent Form
ICH	International Conference on Harmonization
IDE	Investigational Device Exemption
IRI	Interpersonal Reactivity Index
JAMA	Journal of the American Medical Association
LAR	Legally Authorized Representative
LBP	Low back pain
MCIS	minimally clinical important difference
NAMI	National Alliance on Mental Illness
NIH	National Institutes of Health
NIMH	National Institute of Mental Health
NRB	Neurosciences Research Building
ODI	Oswestry Disability Index
OHRE	Office of Human Research Ethics
OHRP	Office for Human Research Protections
PCS	Pain catastrophizing Scale
PFC	Pre-frontal cortex

PHI	Protected Health Information
PI	Principal Investigator
PSEQ	Pain Self-Efficacy Questionnaire
rTMS	repetitive transcranial magnetic stimulation
SAE	Serious Adverse Event/Serious Adverse Experience
SB	Suicidal Behavior
SI	Suicidal Ideation
SMC	Safety Monitoring Committee
SOP	Standard Operating Procedure
SPI	Serial Peripheral Interface
tACS	Transcranial Alternating Current Stimulation
tACS	Transcranial Alternating Current Stimulation
tDCS	transcranial direct current stimulation
tDCS	Transcranial Direct Current Stimulation
TMS	Transcranial Magnetic Stimulation
UE	Unexpected Event
UNC	University of North Carolina
UNC-CH	University of North Carolina at Chapel Hill
US	United States
VAS	Visual Analog Scale

STUDY SUMMARY	
Title	EFFECT OF TRANSCRANIAL ALTERNATING CURRENT STIMULATION IN CHRONIC LOW BACK PAIN: A PILOT STUDY
Short Title	CPS
Protocol Number	17-0870
Phase	Pilot
Methodology	Double-blind, randomized, active sham controlled, cross-over, single site
Study Duration	This study is expected to last 6 months
Study Center(s)	This is a single-site study performed at The University of North Carolina at Chapel Hill.
Objectives (Purpose)	To test the feasibility of using tACS to treat patients with chronic pain, and to collect pilot efficacy and EKG biomarker data for optimizing the design of subsequent large-scale studies. The treatment rationale is to renormalize the presumed pathological structure of alpha oscillations in the prefrontal cortex (PFC) of patients with chronic pain.
Number of Subjects	20
Diagnosis and Main Inclusion Criteria	Eligible participants will be patients who have a diagnosis of chronic pain as defined by a clinician, a >4 on a VAS self-report pain rating, not taking opioids, and have low suicide risk.
Description of Intervention (Procedures/methods)	20 participants will be randomized into one of two arms: to receive either 40 minutes of sham tACS or 40 minutes of 10 Hz tACS during their first stimulation visit (then crossover the next visit) while in a relaxed, yet experimentally controlled state, by watching a nature movie such as "Reefscape" during stimulation.
Related IRB Applications	n/a

1.4 FUNDING SOURCES

Please list below the funding sources for this project:

Sponsor Name	UNC Ramses Number	Sponsor Type	Prime Sponsor Name	Prime Sponsor Type	Sponsor/Grant Number
National Institute of Mental Health (NIMH)	R01MH101547	Federal			

External Funding: This project is externally funded but UNC-CH is not the direct recipient of federal funds.

UNC-CH Funding: This project is not funded through UNC-CH.

Classified: This project is not classified.

2 INTRODUCTION

This document is a protocol for a human research study. This study is to be conducted according to U.S. and international standards of Good Clinical Practice (FDA Title 21 Part 312 and International Conference on Harmonization guidelines), applicable government regulations and Institutional research policies and procedures.

2.1 BACKGROUND

Chronic pain is a severe disabling problem within society, affecting 25-30% of the United States population (Baliki and Apkarian, 2015). The Institute of Medicine estimates that 116 million adults in the United States experience chronic pain, with direct and indirect annual costs totaling over half a trillion dollars (Institute of Medicine Committee on Advancing Pain Research, 2012). Low back pain (LBP) is the second most prevalent cause of disability in US adults and a common reason for lost work days with an estimated 149 million lost days of work per year (Freburger et al., 2011). The lifetime prevalence is as high as 79% in adults (Walker et al, 2004) and 84% in adolescents (Jeffries et al, 2007). The poor rates of recovery (58% at 1 month) and high rates of recurrence (73% in 12 months) contribute to high social and economic costs (Pengel et al., 2003). Chronic low back pain (cLBP) does not have a defined source, and the mechanism of development is not fully understood (Luedtke et al. 2015). In chronic pain the relationship between nociception and pain is often weak or lost indicating abnormal integration and recent neurobiological investigations corroborate the crucial role of the brain by showing substantial structural and metabolic changes (Pioner et al., 2016). It's been hypothesized that in the absence of a peripheral pathology, central sensitization contributes to the development and maintenance of non-specific chronic low back pain (Luedtke et al. 2015). The hypothesized mechanisms are an increased release of excitatory neurotransmitters at spinal level, influencing pain perception via the spinothalamic pathway and altered top down pain control from the brain (Luedtke et al. 2015). Chronic pain is currently extensively studied, but therapeutic options to date are limited, and duration of the symptoms tends to make pain increasingly resistant to treatment. Opioid therapy is helpful in the treatment of acute pain (Ferrari et al. 2015) limited evidence supporting its long-term effectiveness but a growing literature highlighting myriad risks of long-term use, including: misuse, abuse/dependence, overdose, and death (Chou et al., 2015). Deep brain stimulation has shown promising results, but less invasive forms of stimulation also might be effective (Antal et al., 2010). Some studies have shown that both a single session and repeated sessions of repetitive transcranial magnetic stimulation (rTMS) and transcranial direct current stimulation (tDCS) can relieve pain transiently in some patients with chronic pain (Naro et al., 2016, Antal et al., 2010), but others have found the effect to be small and not significant (Jimenez-Torres et al, 2016; Luedtke et al. 2015). Heart rate variability (HRV) is commonly used to assess the autonomic nervous system function and has been shown to predict poor health outcomes (Gockel et al, 2008). Initially developed to evaluate the prognosis of cardiac diseases (Balanescu et al., 2004), heart rate variability (HRV) analysis has been utilized to assess autonomic functions in chronic pain conditions (Staud et al., 2008, Kang et al., 2012). When compared to healthy controls individuals with chronic pain had lower HF (high frequency band) power in HRV representing less parasympathetic output in the altered cardiac autonomic regulation (Södervall et al., 2013). Gockel and colleagues (2008) found a significant association between heart rate variability and perceived

physical impairment in patients with chronic low back pain using Oswestry Disability Index scores. Patients with higher subjective disability had greater sympathetic dominance (lower high frequency band) than patients with minimal perceived disability.

2.2 INVESTIGATIONAL AGENT

One alternative not yet explored is Transcranial Alternating Current Stimulation (tACS). tACS is a safe, non-invasive, easy-to-administer procedure that applies weak electrical currents to the scalp to modulate rhythmic brain activity patterns. In addition, the [name] Lab has used this technology in clinical trials to treat individuals with serious mental illness, such as depression and schizophrenia ([name] 2015, [name] et al., 2016). Previous research has demonstrated that tACS enhances alpha oscillations in healthy participants (Zaehle et al., 2010) and may thus help to renormalize the presumed pathological structure of alpha oscillations in the pre-frontal cortex (PFC) of patients with chronic pain (Lustenberger et al., 2015).

Therefore, tACS may be an important next step in treating chronic pain. As stated above, some patients are resistant to other therapies including medications or in too much pain to do physical therapy. Treatment with tACS may provide an alternative for patients with disabling chronic pain who have few options.

2.3 DOSE RATIONALE

Previous studies have shown a relationship between alpha oscillations (8-12 Hz) and attention (Cooper et al., 2003), arousal, and emotion (Weinreich, Stephani, & Schubert, 2016; Gaeta et al., 2015). The substantial comorbidity of chronic pain and mental disorders and the close relationship between chronic pain and psychological factors indicates that brain dysfunction plays a central role in the development and maintenance of chronic pain (Pioner et al., 2016). Pain stems from dynamic interactions between sensory and contextual (i.e., cognitive, emotional, and motivational) processes that are mediated by feed-forward and feedback processes in the human brain. Alpha/beta oscillations are linked to the feedback process and a suppression of oscillations at alpha frequencies is associated with tonic pain. Previous studies in chronic pain have found an increase of theta oscillations, slowing of the peak alpha frequency, and increase in beta oscillations in the frontal areas (Lim et al., 2016). These changes along with the alpha-gamma oscillation coupling having a strong pain predictive model (Pioner et al., 2016) provide evidence alpha oscillations play an important role in chronic pain. Our proposed intervention of transcranial alternating current stimulation (tACS) at the alpha frequency (~10 Hz) has been shown to alter alpha oscillations with sustained effects (Kasten, Dowsett, & Herrmann, 2016). These data suggest that α -tACS at 10 Hz applied to the prefrontal cortex could potentially alleviate many of the symptoms associated with chronic pain. While there is currently no literature in HRV response to tACS, a study in progress is investigating HRV during tACS in healthy individuals. Since tDCS has been shown to increase parasympathetic and decrease sympathetic activity (Montenegro et al., 2011) we hypothesize that tACS will also increase parasympathetic activation specifically the high frequency bands.

2.4 STUDY AIMS/HYPOTHESES

2.4.1 PRIMARY OBJECTIVE

NULL HYPOTHESIS. There is no difference in parasympathetic tone in Heart Rate Variability, shown by an increase in high frequency input via spectral analysis on EKG recordings between active and sham stimulation.

ALTERNATIVE HYPOTHESIS. There is a difference in parasympathetic tone in Heart Rate Variability, shown by an increase in high frequency input via spectral analysis on EKG recordings between active and sham stimulation.

2.4.1 SECONDARY OBJECTIVE

NULL HYPOTHESIS. There is no difference in self-reported perceived pain rating between baseline and the active stimulation.

ALTERNATIVE HYPOTHESIS. There is a difference in self-reported perceived pain rating between baseline and active stimulation.

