5.1.2 INITIAL SCREENING SESSION (VISIT 1)

At day 1 of stimulation, participants will be guided through the consent form and the HIPAA authorization form and be given the time to ask any questions about the information discussed. To ensure that all aspects of the research are understood, participants may be asked a series of questions about the research they are about to take part in (*Appendix E*). Once it is clear that the participant understands the consent form and HIPAA authorization, they may sign the forms.

Following the consent process, the participant completes the ODI and DVPRS to measure disability and pain intensity on 0-11 scale. The HAM-D and DASS-21 will assess low suicide risk and depression level. The self-report measures: UCLA Activity Score, PCS, and PSEQ will assess physical activity limitations, pain experience, and confidence in daily activities. Data on demographics, handedness, stai, bis-bas, and opinion pre-treatment will also be collected.

Once eligibility has been confirmed and all relevant data collected, Day 1 of stimulation will begin.

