5.2.2 DAYS 2 OF STIMULATION (VISIT 2)

Prior to starting any study procedures, female participants will be asked to take a urine pregnancy test to ensure continued eligibility. The ODI, DVPRS, 5xSST, FTF, and pressure pain threshold test will be administered before stimulation. A resting state EEG will be recorded for 5 min before and after stimulation. The participant will receive 40 minutes of sham or 10 Hz tACS stimulation (as per the initial randomization) while watching “Reefscape”. The stimulation will be followed by the pressure pain threshold, 5xSST, FTF, stimulation adverse effects questionnaire and perceived improvement ending the session.

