5.3 FOLLOW-UP

5.3.1 FOLLOW-UP EMAIL

Two days after both sessions of stimulation, participants will receive an email with a follow up survey to assess any change in pain perception. The ODI and DVPRS will take approximately 15 minutes to complete.

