6.3 SPECIAL ASSAYS OR PROCEDURES

6.3.1 SPECIAL PROCEDURES

Each participant will attend two days of stimulation for this study. Each participant will be randomly assigned to one of two treatment arms (sham or 10 Hz tACS) then the opposite on the second visit. For more information on the stimulation procedures, see section 7.2 *Preparation and Administration of Study Investigational Product*.

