11 STATISTICAL PLAN

11.1 STATISTICAL ANALYSIS STRATEGIES

Our study design is a AB/BA crossover and we will ensure a washout effect by scheduling 1-3 weeks between stimulation sessions. A continuous outcome approach will be used to analyze the crossover trial data where carryover effects will be assumed to be equal.

Primary outcome: Use kubios software to analyze HRV over before and after stimulation. A standard spectral analysis will be applied to the pre and post intervals, including total power, HF, LF, and HP. Specifically looking at the HF component since it reflects the parasympathetic modulation of the heart rate. Use a repeated measure ANOVA with factor session (1 vs 2) and factor treatment (active vs sham) (R software). We hypothesize a treatment main effect and with no session effect and no interaction.

Secondary outcome: A Mann-Whitney-Wilcoxon rank-sum testMann Whitney U test (R software) will be performed on the self-report VAS pain scale (nonparametric scale) (from DVPRS) before and after stimulation as well as between sessions to analyze any differences in self-report perceived pain. Grouped ANOVAs and unpaired t-tests may also be used to analyze correlations within other self-report measures

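### The secondary pain hypothesis compares baseline with active stimulation and leaves out sham, so a fall in pain shared by both conditions would reject it with no tACS effect

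*Combined protocol and SAP*

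**What the plan says.** Section 2.4.1, Secondary Objective, gives the null as "There is no difference in self-reported perceived pain rating between baseline and the active stimulation". The alternative uses the same two terms. The Primary Objective just before it is framed differently: its contrast is in "spectral analysis on EKG recordings between active and sham stimulation".

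Section 6.3.1 describes the crossover: "Each participant will be randomly assigned to one of two treatment arms (sham or 10 Hz tACS) then the opposite on the second visit".

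For pain, Section 11.1 plans a rank-sum test "before and after stimulation as well as between sessions to analyze any differences in self-report perceived pain". For the primary outcome the same section specifies a repeated-measures ANOVA with "factor session (1 vs 2) and factor treatment (active vs sham").

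The pain ratings are scheduled as follows:
- **Visit 1, before stimulation (Section 5.1.2):** "the participant completes the ODI and DVPRS to measure disability and pain intensity on 0-11 scale".
- **Visit 2 (Section 5.2.2):** "The ODI, DVPRS, 5xSST, FTF, and pressure pain threshold test will be administered before stimulation".
- **After each visit (Section 5.3.1):** "Two days after both sessions of stimulation, participants will receive an email with a follow up survey to assess any change in pain perception". This survey contains the DVPRS and is the only DVPRS scheduled after stimulation.

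**The concern.** The sham session exists to remove whatever change in pain would have occurred without the active current: placebo response, natural fluctuation, and regression to the mean after selecting people with VAS above 4. The stated hypothesis makes no use of it.

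Section 11.1 does not clearly repair this. If session means 1 versus 2, as it does for the primary outcome, each session contains active stimulation for one sequence and sham for the other. The comparison then tests a period effect. A sham before-after test might be run beside the active one, but two separate before-after tests are not a test of the difference between them.

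The baseline is also not pinned down. It could be the Day 1 rating or the pre-stimulation rating of the active session.

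The Study Summary makes pilot efficacy data for later trials an objective, and Section 11.2 says the results will set future sample sizes. An uncontrolled change would carry the non-specific response into that planning.

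**Working it through.** The plan gives no power, alpha, effect size or SD for pain, so there is no figure to reproduce.

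**1. What each contrast estimates.** Let *c* be the fall common to both conditions, *t* the extra fall due to tACS, and *p* any extra change in session 2 relative to session 1. Assume 10 participants per sequence and equal carryover (the latter is the assumption in Section 11.1).

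- *Before versus after active:* mean change = −c − t + p/2. With t = 0 and p = 0 this is −c, so the stated null is false whenever c is not zero.
- *Session 1 minus session 2 change:* treatment contributes (−t × 10/20) − (−t × 10/20) = 0. For t = 2 this is −1 − (−1) = 0. Only −p remains.
- *Session 1 change minus session 2 change, compared between sequences:* active-first gives (−c − t) − (−c + p) = −t − p. Sham-first gives (−c) − (−c − t + p) = t − p. The difference is −2t, and both c and p drop out.

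**2. Size, by simulation.**
- From the documents: n = 20, AB/BA design, entry at VAS >4 (Section 3.1), DVPRS MCID of 2 points (Section 6.1).
- Assumed: mean pain 5 or 6, SD 2, common correlation 0.5 or 0.7 among the four ratings, scores rounded and limited to 0-10, the entry rule applied to the Day 1 rating, 10 per sequence, two-sided alpha 0.05.
- There were 20,000 trials per scenario, using the rank-sum test with tie and continuity correction. Ranges cover the four mean-by-correlation settings.

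Chance of rejecting baseline = active with **zero** tACS effect:

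| Shared fall (points) | Baseline = active session's own pre-rating | Baseline = Day 1 rating |
|---|---|---|
| 0 | 0.5-4.4% | 1.1-18.0% |
| 0.5 | 9.5-26.1% | 17.0-57.8% |
| 1 | 49.7-66.7% | 65.0-90.7% |
| 1.5 | 86.0-95.6% | 94.9-99.3% |

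In the same cases the between-sequence comparison of period differences rejects in 4.1-4.6%. With a true 2-point tACS effect it rejects in 82.4-95.8%.

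A rank-sum comparison of session 1 and session 2 changes rejects in 3.1-12.2% with that 2-point effect and in 7.1-17.4% with none, so it does not detect treatment.

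**3. Sensitivity to the entry rule.** Without truncation at VAS >4 (mean 6, SD 2, correlation 0.4-0.8, 3,000 trials per scenario, zero tACS effect), before versus after active rejects as follows:
- 1-point fall: 21-28% by rank-sum, 46-88% by the paired signed-rank test.
- 2-point fall: 90-97% by rank-sum, 96-100% by signed-rank.

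A signed-rank test of active change minus sham change stays at 4.2-5.4%.

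Paired normal check at correlation 0.6 and a 1-point fall: SD of the difference = 2 × √(2 × 0.4) = 1.79; standard error = 1.79/√20 = 0.40; 1/0.40 − 1.96 = 0.54; Φ(0.54) = 71%. Over correlations 0.4-0.8 the same formula gives 53-94%.

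**The case against.** The best defence is that Section 11.1 opens by calling the data crossover data and assuming equal carryover, before it turns to either outcome. That assumption serves a purpose only in a treatment contrast across periods. Each participant has one active and one sham session, so a comparison between sessions may simply be loose wording for active versus sham. This is a fair reading, but the section does not say so. Even if it were intended, the test would not match the hypothesis in Section 2.4.1, and the two would need reconciling.

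Appendix A marks baseline assessments only at the first stimulation visit, which favours Day 1 as the baseline. That does not help, because Day 1 gives the higher false rejection rates.

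The magnitudes are fragile. The size of the shared fall is wholly assumed. With an own-session baseline, regression to the mean alone produces a mean fall of only 0.12-0.33 point and does not push the rank-sum test above 5%. For a 1-point fall with that baseline, the rank-sum figure is 50-67% with the entry rule applied to the Day 1 rating and 21-28% without it. Applying the rule is reasonable, since Section 11.1 takes the VAS from the DVPRS and eligibility is confirmed after the Day 1 DVPRS, but the documents do not name the rating that decides entry. The simulation also uses 0-10, where Section 5.1.2 says 0-11.

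Finally, this is a secondary outcome in a 20-person pilot, and the data for a controlled comparison will exist anyway. That makes the fault easy to correct, but it does not make the stated hypothesis right.

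**Conclusion.** The concern holds. As written, the secondary hypothesis can be rejected by any fall in pain that active and sham share, and no section states an active-versus-sham test for pain. That conclusion follows from the algebra and needs no numerical assumption.

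The size does rest on assumptions. For a 1-point shared fall, zero tACS effect and an own-session baseline, the planned rank-sum test rejects in roughly 21-67% of trials, depending on whether the entry rule truncates the Day 1 rating. With Day 1 as baseline and the entry rule applied, the figure is 65-91%. The controlled contrast holds close to 5% throughout.

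**What to change.** Restate the secondary hypothesis in Section 2.4.1 as no difference between active and sham in the change in DVPRS pain from that session's pre-stimulation rating to its two-day follow-up rating. This also settles what baseline means.

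In Section 11.1, replace the comparison between sessions with one between active and sham, adjusting for session. For each participant, take the session 1 change minus the session 2 change, and compare these values between the two sequences with the rank-sum test already planned. A mixed model with treatment and period would also serve. Keep the active before-after change as a descriptive summary. Make the change before unblinding, so that the contrast is not chosen after the fact.

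Only wording in these two sections changes; no visits, ratings or participants are added. The cost is precision: under the simulation assumptions with the entry rule, power for a true 2-point effect with no placebo fall is 83-96%, against 98-100% for the uncontrolled before-after test.

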3 SUBJECT SELECTION AND WITHDRAWAL

A total of 20 participants will be recruited for this study and all data will be collected at UNC-CH. No specific plans have been made to enroll participants from vulnerable populations.

